#### **Primary Efficacy Analysis**

##### **Primary Efficacy Analysis of PFS**

The primary analysis of PFS will be based on investigator assessment using the AT population. Time to radiographic progression or death is the primary efficacy analysis and will be performed using a stratified (by prior treatment) log-rank test.

A log-rank test stratified by prior mTOR therapy and prior immune therapy will be used to test the null hypothesis of no difference between dalantercept plus axitinib and placebo plus axitinib using a one-sided 0.10 significance level. Kaplan-Meier curves will be displayed depicting each treatment group. The hazard ratio (dalantercept plus axitinib: placebo plus axitinib) will be estimated using a stratified Cox proportional hazards model along with the 95% confidence intervals. Multiple sensitivity analyses will be outlined in the SAP. Each sensitivity analysis will be analyzed using the same statistical analyses; however, the PFS definition may differ. One such sensitivity analysis will include patients going off-study for symptomatic progression,

change in cancer treatment, or decreasing performance status which will be considered as PFS events at that known date.

The mode of radiologic assessment should be the same across visits within each patient. Screening/Baseline tumor assessments must be performed prior to randomization and within the screening period. When multiple radiographic tumor assessments are performed prior to randomization, the closest assessment prior to that date will be designated as baseline.

#### **Missing Radiological Assessments and Non-evaluable (NE) Designation**

If all lesions cannot be evaluated due to missing data or poor image quality the patient is not evaluable (NE) at that time point. If only a subset of lesions can be evaluated at an assessment, the visit is also considered NE.

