### **15.4. Part 2 – Efficacy and Safety**

#### **15.4.1. Primary Endpoint**

**Progression free survival:** PFS is the primary endpoint in Part 2 and will be defined as the date of radiographic (also called documented) tumor progression (per RECISTv1.1) or death from any cause, whichever is earliest, minus date of randomization (or first date of dosing in Part 1 as will be implied throughout) plus one day. The term “on-study” will refer to the period from randomization until 28 days after last dose of study medication. Patients will be censored (i.e., those patients not exhibiting radiographic tumor progression or death) on the date of the last tumor assessment on-study and includes:

- Those patients discontinuing study medication due to any reason and having at least 1 radiographic tumor assessment before or on the date of discontinuation
- Those patients in whom radiographic tumor progression or death occurs following  $\geq 2$  consecutive scheduled missing radiographic tumor assessments
- Those patients given non-study antitumor medication or treatment prior to documentation of radiographic tumor progression

Patients missing baseline radiographic tumor assessments will be censored on the date of randomization. Patients with missing post-randomization radiographic tumor assessments will be censored on the date of randomization unless death occurred prior to the first and second scheduled radiographic tumor assessment, whereby death is the event.

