## 23. APPENDICES

### 23.1. Appendix 1: RECIST v. 1.1

#### RECIST Criteria-Response Evaluation

Evaluation of target lesions	
Complete Response (CR)	Disappearance of all target lesions. Any pathological lymph nodes (whether target or non-target) must have reduction in short axis to < 10 mm.
Partial Response (PR)	At least a 30% decrease in the sum of diameters of target lesions, taking as reference the baseline sum diameters.
Stable Disease (SD)	Neither sufficient shrinkage to qualify for PR nor sufficient increase to qualify for PD, taking as reference the smallest sum diameters while on study.
Progressive Disease (PD)	At least a 20% increase in the sum of diameters of target lesions, taking as reference the smallest sum on study (this includes the baseline sum if that is the smallest on study). In addition to the relative increase of 20%, the sum must also demonstrate an absolute increase of at least 5 mm. (Note: the appearance of one or more new lesions is also considered progression).
Evaluation of non-target lesions	
Complete Response (CR)	Disappearance of all non-target lesions and normalisation of tumour marker level. All lymph nodes must be non-pathological in size (< 10mm short axis).
Non-CR/Non-PD	Persistence of one or more non-target lesion(s) and/or maintenance of tumour marker level above the normal limits.
Progressive Disease (PD)	Unequivocal progression (see comments below) of existing non-target lesions. (Note: the appearance of one or more new lesions is also considered progression).

Please refer to the Study Reference Guide for details on RECIST v. 1.1.

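### The non-evaluable rule in section 15.4.1 has no exception for progression, so a partly readable scan with a new lesion is both a PFS event and NE

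*Combined protocol and SAP*

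**What the plan says.** Section 15.4.1 (Primary Endpoint) sets the event date as the "date of radiographic (also called documented) tumor progression (per RECISTv1.1) or death from any cause, whichever is earliest". Nothing there requires every lesion to be readable.

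Appendix 1 gives three routes to progression:
- Target lesions: "At least a 20% increase in the sum of diameters of target lesions, taking as reference the smallest sum on study", together with an absolute increase of at least 5 mm.
- Non-target lesions: "Unequivocal progression (see comments below) of existing non-target lesions".
- New lesions: "the appearance of one or more new lesions is also considered progression".

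The paragraph of section 15.4.1 on missing assessments and the NE designation then states: "If only a subset of lesions can be evaluated at an assessment, the visit is also considered NE". The label applies to the whole visit.

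Two censoring rules in section 15.4.1 bear on the result. One censors "Those patients given non-study antitumor medication or treatment prior to documentation of radiographic tumor progression". The other censors patients whose event follows two or more "consecutive scheduled missing radiographic tumor assessments".

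The reads that count are the site's: "The primary analysis of PFS will be based on investigator assessment using the AT population". Section 11.4.1 says the same.

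**The concern.** Take a scan on which one target lesion cannot be measured but a new lesion is plainly seen. The endpoint definition and Appendix 1 make it a progression on that date. The NE paragraph makes it a visit with no usable assessment. Two programmers working from this text could code the primary endpoint differently for the same patient.

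At stake are the dating and counting of primary events. If the NE rule governs, progression is not documented on that scan. The event is then picked up later, or the patient is censored although progression was visible. Censoring of that kind would be informative, because it follows from the progression itself.

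There is also a smaller gap. The text does not say whether an NE visit counts as a missing assessment under the rule for two or more in a row. That is missing detail, and the main point does not depend on it.

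**Working it through.** **1. The rules side by side, for a scan with a new lesion and one unreadable target lesion**

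| Rule | Condition | Result |
|---|---|---|
| 15.4.1, Primary Endpoint | Progression per RECIST v1.1 | Event on scan date |
| Appendix 1 | New lesion present | Progression |
| 15.4.1, NE paragraph | Not all lesions readable | Visit is NE |

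Unequivocal non-target progression gives the same conflict. Reading the NE paragraph as covering baseline lesions only does not help, because the label still falls on the whole visit.

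**2. Is precedence stated elsewhere?** Section 11.4.2 refers to the full RECIST guideline, Appendix 1 to the Study Reference Guide, and section 15.1 to a separate SAP. These are general referrals and rank neither rule above the other. Section 15.6 treats departures from the protocol's analyses as deviations to be declared, so the default is the protocol as written.

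**3. What happens if the NE rule is applied**
- *Treatment continues.* The next scheduled scan (section 12.2) is 6 weeks later through C15: 42 days, 42/30.44 = 1.38 months. After C15 it is 12 weeks later (C15D1 to C19D1 = 4 × 21 = 84 days, 2.76 months).
- *Treatment stops and the visit is treated as NE throughout.* The final-visit scan is still due, because progression has not been confirmed (Schedule of Events, footnote 17).
- *Non-study antitumor therapy starts before a later scan.* The patient is censored under section 15.4.1, and section 12.2.2 waives the 3-monthly scans.
- *The site calls progression but the analysis codes NE.* Treatment stops (section 9.1), and neither the final-visit scan (section 12.2.1) nor follow-up scans (section 12.2.2) are required. The patient could be censored with no later scan to recover the event.

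**4. The plan's own event count.** Inputs from section 15.2: HR = 5/8 = 0.625, one-sided alpha 0.10, power 80%, 1:1 allocation (section 9.1).

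d = 4(1.2816 + 0.8416)² / (ln 0.625)² = 81.6, so 82 events. Power at 82 is 80.1%. The stated figure reproduces.

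**5. Delay per event censored instead of counted.** Assumptions: exponential PFS with medians 5 and 8 months, 65 patients per arm, uniform accrual over A months, dropout hazard η. With λ = ln 2/median and k = λ + η, expected events at time t after accrual ends are

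E(t) = Σ over arms of (65/A)(λ/k)[A − (e^(−k(t−A)) − e^(−kt))/k];

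while accrual is still open, replace A by t inside the square bracket. The delay is T(83) − T(82), where T(n) solves E(t) = n.

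| Accrual (months) | Delay, η = 0 | Delay, η = 0.02 per month |
|---|---|---|
| 12 | 0.197 | 0.291 |
| 18 | 0.196 | 0.289 |
| 24 | 0.201 | 0.288 |

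That is about 6 days without dropout and about 9 days with it. It applies only to events lost to censoring, not to events that are re-dated. Because the analysis waits for 82 counted events, the cost is time rather than power.

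**6. Check of the target-lesion clause in the proposed fix.** The clause counts unread target lesions as zero, so the evaluated sum is at most the full sum. The smallest complete sum on study is at least the true smallest sum. If the evaluated sum exceeds the reference by 20% and 5 mm, the full sum must too. Example: smallest sum 20 + 80 = 100 mm, threshold 120 mm.
- Only the first lesion is readable, now 26 mm. It has grown 30%, but 26 < 120, so the visit stays NE. With the other lesion unchanged the full sum is 106 mm (+6%), not progression.
- Only the second lesion is readable, now 125 mm. 125 against 100 is +25% and +25 mm, so it is progression whatever the unread lesion measures.

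In 738,804 simulated partly readable visits (2 to 5 target lesions) the clause gave no false progression. Comparing the readable lesions only with their own earlier sum gave 77,162.

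**The case against.** The strongest reply is that the plan largely protects itself. The primary analysis uses the site's reads, the event is progression per RECIST v1.1, and no step is described that would overturn a progression called by the site. Harm needs someone to apply the NE sentence against an investigator who has called progression, or an investigator who sees a new lesion and still codes NE. The NE paragraph can also be read as a label for visits where status cannot be established, and a new lesion that is seen has, in a sense, been evaluated. The RECIST guideline, the Study Reference Guide or the separate SAP may settle the matter. The size is unknown and probably small, and a full-interval shift is only one scenario: section 11.4.1 wants absence of progression determined before the next cycle, which an NE visit does not do.

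Most of this stands as a limit on the size. It does not remove the conflict. The sentence labels the whole visit without exception, so the charitable reading is one the text does not state. If site progressions are counted regardless, the NE sentence is not being followed, and the plan should say so. It is also fair that one precedence clause would settle the core of the problem, and that the check in step 6 supports the proposed remedy and is not evidence of the fault.

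**Conclusion.** The concern holds: the NE sentence is wrong as written, because followed literally it would mis-date or censor real primary events. It should be corrected.

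Per affected patient who stays on treatment, the event moves by 42 days through C15 or 84 days after it. Per event censored instead of counted, the 82-event trigger moves by about 6 days, or about 9 days with 2% monthly dropout. The delay figures rest on the assumed exponential medians of 5 and 8 months, 65 per arm, and uniform accrual over 12 to 24 months. The number of affected scans cannot be derived from the documents. No loss of power and no bias between arms is claimed. Confidence is high on the textual conflict. The practical effect depends on how sites and programmers handle these scans.

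**What to change.** Replace the second sentence of the NE paragraph in section 15.4.1 with:

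> *When some but not all lesions are readable, the visit is progression on that date if there is a new lesion, if non-target lesions have unequivocally progressed, or if the readable target lesions alone (unread ones counted as zero) sum to at least 20% and at least 5 mm above the smallest complete target-lesion sum on study. Otherwise the visit is NE.*

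The minimum is a single clause stating that progression per RECIST v1.1 established on a partly readable scan takes precedence over NE. The longer form is better because it also settles the target-lesion case.

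Add one sentence saying whether an NE visit counts as missing under the rule for two or more consecutive missing assessments.

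The cost is two sentences in section 15.4.1, carried into the SAP while the trial is still blinded. No new scans or visits are needed. The target-lesion clause uses lesion-level measurements, so confirm that the CRF records them, since the documents do not describe those fields.

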#### **Assessment of Potential Influential Prognostic Factors of PFS and OS**

In addition to the analyses described above, the following pre-specified prognostic variables will be examined for their influence alone and in combination with the treatment effect on the analysis of PFS.

- Number of sites of metastatic disease;
- Prior nephrectomy;
- ECOG performance status 0 or 1, and
- International Metastatic Renal Cancer Database Consortium (IMDC) and Memorial Sloan Kettering Cancer Center (MSKCC) risk groups both categorized as favorable, intermediate, or poor.

#### **15.4.2. Secondary Endpoints**

**Secondary endpoint:** PFS in the subgroup of the patients who had 2 or more prior lines of anticancer therapy will be analyzed similarly as the primary PFS analysis. Due to the size of the subgroup, the comparison will be tested at one-sided 0.20 significant level.

If the hazard ratio is 0.625, the same as the PFS hypothesis for overall population, the power to claim statistical significance will be 80% if the subgroup has 52 events and 70% with 34 events.

**Safety Analysis:** The safety analyses will be performed on the AT population. Adverse event incidence rates will be tabulated by System Organ Class (SOC) and preferred term and without regard to causality. The frequency of occurrence of overall toxicity, categorized by toxicity grades, will be summarized. Shift tables and change from baseline will be summarized by analyte for laboratory panels. Treatment-emergent laboratory findings will be summarized. Change from baseline and shift tables may be presented for vital sign and ECG parameters.

**Overall Survival (OS):** Another key secondary endpoint that will be estimated is OS. OS is defined as the time from randomization to death. If the trial is concluded and there is no evidence that the patient died, then the patient will be censored at the last follow-up contact visit for which the patient is documented as being alive. If the patient is lost to follow-up, all reasonable effort will be made to ascertain the patient status. Patients who discontinue from the treatment phase of the study will be followed for at least two years from randomization for OS. Median survival along with quartiles and confidence intervals will be calculated.

A Kaplan-Meier curve for survival will be displayed and 95% confidence intervals for median survival computed for each treatment arm. A stratified log-rank will be used to test the difference in OS between the two treatment arms. The hazard ratio for the OS treatment effect will be estimated using a stratified Cox model.

**Objective Response Rate (ORR):** Patients will be evaluable for ORR if they have at least one measurable lesion at baseline and at least one radiographic disease assessment after baseline. The Best Overall response rate will be estimated based on the proportion of patients evaluable for response. Exact 95% confidence intervals will be calculated.

**Duration of Response (DR):** Duration of response is defined as the time from the first radiographic tumor response of CR or PR to the date of radiographic tumor progression or death, whichever is earliest.

**Disease Control Rate (DCR):** Disease control rate will be estimated as the proportion of patients evaluable for response who meet the criteria for CR, PR, or SD. The 95% confidence intervals of disease control rate will be calculated.

**PD Biomarkers (Exploratory):** Levels of BMP9/10, ALK1 and other relevant markers in tumor tissue and blood will be summarized, and analyzed for correlation with efficacy outcome measures.

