## **14.5. Documentation and Methods of Reporting of Adverse Events by Investigator**

Patients will be evaluated and questioned generally for AEs during the course of the study, starting at the signing of the informed consent. All non-serious AEs occurring after signing of the ICF until a patient is dosed on C1D1 are to be documented on the medical history CRF. All AEs occurring after the C1D1 dose through 30 days after the last study drug administration (final visit) are to be documented on the AE CRF.

All AEs spontaneously reported by the patient and/or in response to an open question from study personnel or revealed by observation, physical examination or other diagnostic procedures will be recorded on the AE CRF. Any clinically relevant changes in laboratory assessments, or other clinical findings as described in [Section 14.1](#), are considered AEs and must be recorded on the AE CRF. AEs are to be followed for resolution as described in [Section 14.6](#).

It is important that each AE report include a description of the event, duration (onset and resolution dates), severity, relationship with dalantercept/placebo, relationship with axitinib, any other potential causal factors, any treatment given or other action taken (including dose modification or discontinuation of dalantercept or axitinib) and outcome. In addition, SAEs should be identified and the appropriate seriousness criteria documented. Adverse events categorized as SAEs must also be documented using an SAE Report Form as described in [Section 14.5.1](#).

Specific guidance can be found in the CRF Completion Guidelines provided by the sponsor or designee.

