### 15.2. Determination of Sample Size

#### Part 1

There is no formal sample size calculation for Part 1 (dose escalation and expansion).

#### Part 2

The primary analysis of efficacy will be performed when at least 82 PFS events have been observed and documented. If the median time to PFS is assumed to be 5 months in the placebo plus axitinib control group, then a total of 82 PFS events will provide approximately 80% power to detect a 3 month extension from 5 to 8 months in the dalantercept plus axitinib experimental treatment group when performing a stratified log-rank test of the null hypothesis of no difference between treatment groups using a one-sided 10% significance level.

The projection of power is made under a proportional hazards assumption so that the hazard ratio (HR) for dalantercept plus axitinib relative to placebo plus axitinib is equal to 0.625 under the alternative hypothesis. It is projected that 130 patients will need to be randomized to obtain 82 PFS events. The number of patients to be randomized provides for patient censoring patterns that could occur under the alternative hypothesis in the event the dropout rate is higher than expected in either treatment group.

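### Part 2 adverse events are summarised only as incidence and grade-frequency tables, with nothing that accounts for time at risk, although treatment is tied to progression and the design assumes median PFS of 5 versus 8 months

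*Combined protocol and SAP*

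**What the plan says.** Section 8 (Trial Objectives) makes safety and tolerability of the combination a secondary objective of Part 2. Section 15.4.2 (Secondary Endpoints, Safety Analysis) gives the AE summaries, in the All Treated population: "Adverse event incidence rates will be tabulated by System Organ Class (SOC) and preferred term and without regard to causality", and "The frequency of occurrence of overall toxicity, categorized by toxicity grades, will be summarized". It names no patient-time denominator, time-to-first-event analysis or fixed-window summary.

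Three other places determine how long a patient is at risk of a recorded AE:

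- Section 9.1: Part 2 treatment stops at RECIST progression or when either dalantercept/placebo or axitinib is discontinued.
- Section 14.5: the events to be documented on the AE form are described as "All AEs occurring after the C1D1 dose through 30 days after the last study drug administration (final visit"), so the collection window lengthens with treatment.
- Section 15.2: the sample size is set to "detect a 3 month extension from 5 to 8 months in the dalantercept plus axitinib experimental treatment group".

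Section 15.5 mentions exposure/toxicity relationships, but as a pharmacokinetic analysis in the PK population, which requires at least one dose of dalantercept. It concerns drug exposure and does not compare the arms on time at risk. Section 15.1 leaves further detail to a separate SAP.

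**The concern.** A crude percentage with at least one event depends on both the event hazard and how long patients were observed. If dalantercept delays progression as hoped, its patients stay on treatment longer, have a longer AE window, and accumulate more first events even when the hazard is the same in both arms. An effective drug then looks more toxic than it is.

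The opposite is also possible. Table 3 in Section 10.6.1 ends dalantercept/placebo for grade 3 or higher cardiovascular events and for most grade 2 or higher bleeding. Section 9.2.1 reports fluid overload as the Phase 1 dose-limiting toxicity. If such events shorten treatment on dalantercept, crude incidence would make it look safer than it is. The direction of the bias is therefore not known in advance. At stake is how the two-arm AE tables are read for the Part 2 safety objective.

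**Working it through.** **Inputs from the documents (Section 15.2).** Median PFS is 5 months on control ("If the median time to PFS is assumed to be 5 months in the placebo plus axitinib control group") and 8 months on dalantercept, with a hazard ratio "relative to placebo plus axitinib is equal to 0.625 under the alternative hypothesis". There are 82 events, 130 patients (65 per arm, Section 9.1) and a test "using a one-sided 10% significance level".

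**Reproducing the plan's own figure.** Events = 4 × (1.2816 + 0.8416)² / (ln 0.625)² = 18.03 / 0.2209 = 81.6, that is 82. Power at 82 events is 80.1%. The median ratio is 8/5 = 1.6, the inverse of 0.625. The PFS design figures are internally consistent.

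**Assumptions, not in the documents.** Time on treatment T is exponential and ends at the PFS event. The AE window is T plus 1 month. The AE hazard λ per month is constant and the same in both arms. Placebo incidence is 10, 20 or 30%. The rates at which treatment ends are μ = ln 2/5 = 0.1386 and ln 2/8 = 0.0866 per month.

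**A. All patients followed until they stop treatment.** Crude incidence = 1 − exp(−λ) × μ/(μ + λ). Solve λ from the placebo value, then apply it with the dalantercept μ.

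| Placebo | λ per month | Dalantercept | Gap (points) |
|---|---|---|---|
| 10% | 0.0134 | 14.5% | +4.5 |
| 20% | 0.0296 | 27.6% | +7.6 |
| 30% | 0.0498 | 39.6% | +9.6 |

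**B. Observation stops at 82 PFS events.** With equal follow-up A and no dropout, 65(1 − exp(−0.1386A)) + 65(1 − exp(−0.0866A)) = 82 gives A = 9.1 months (46.6 + 35.4 events). The other 130 − 82 = 48 patients have no event yet. Incidence by A = 1 − exp(−λ) + [λ exp(−λ)/(λ + μ)] × [1 − exp(−(λ + μ)(A − 1))].

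| Follow-up pattern | 10% | 20% | 30% |
|---|---|---|---|
| Equal follow-up, 9.1 months | +1.6 | +3.0 | +4.2 |
| Uniform accrual over 12 months (assumed) | +1.7 | +3.2 | +4.5 |
| Uniform accrual over 18 months (assumed) | +1.9 | +3.6 | +4.8 |

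**C. Relaxing the other assumptions, with the follow-up of A.** Gaps at 10/20/30% placebo incidence, in points (these rows use a 30-day window in place of 1 month):

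- Equal other-cause discontinuation of 0.04 per month: +3.0/+5.2/+6.7.
- Other-cause discontinuation of 0.02 per month on control and 0.06 on dalantercept: +0.6/+1.1/+1.5.
- AE risk confined to the first 2 months: +0.1/+0.2/+0.3.

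**D. Reversal.** Assume instead a median treatment time of 3 months on dalantercept and 5 on placebo, with the model of A. Equal hazards give 6.7/13.9/21.7% on dalantercept against 10/20/30%. A true 1.5-fold hazard gives 9.8/19.8/29.9%, so a real excess would not show.

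**The case against.** A reader might infer that the plan expects dalantercept patients to be treated 60% longer. It does not say so. The factor of 1.6 applies to median PFS under the alternative hypothesis only. Treatment also ends when either drug is stopped, after most dosing delays beyond 3 weeks, and for prohibited medication. No treatment duration by arm is stated.

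A reader might also take 4 to 10 points as the expected distortion. That range needs essentially everyone off treatment when safety is reported. At the planned 82-event cut the model gives about half as much. With 65 per arm, the gaps in table A are only 0.8 to 1.2 standard errors, with 95% half-widths of 11 to 16 points.

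Nor do the documents plan a formal between-arm AE test; the rates are tabulated. The separate SAP, whose text is not in the material reviewed, could add time-adjusted summaries. Finally, a rate per patient-month is no cure-all: for early-onset toxicity the longer-treated arm adds low-risk months, which dilutes its rate.

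All of these stand as limits on the size, the wording and the remedy. They do not remove the point. The protocol names its safety tables, a two-arm table serving a safety objective will be read as a comparison, and possible early stopping on dalantercept makes the sign of the bias uncertain without making crude incidence neutral.

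**Conclusion.** The concern holds in a limited form: the protocol names no AE summary that accounts for time at risk, in a design where time at risk may well differ by arm. The 2-to-5-point and 4-to-10-point ranges (tables B and A) are conditional on treatment time following PFS, a constant and equal AE hazard, and placebo incidence of 10 to 30%. The documents give no AE rate, onset pattern or treatment duration against which to check these. The primary PFS test, the sample size and the decision rules are unaffected. This is a worthwhile improvement to safety reporting, not an error in the efficacy plan.

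**What to change.** Keep the crude incidence and grade tables. In Section 15.4.2 or the SAP, add:

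1. Cumulative incidence of first event by arm at fixed times, for example 12 and 24 weeks, for edema/weight gain, pulmonary edema, ejection fraction decrease, bleeding and anemia. State how death and the end of AE collection are handled. Treating the end of collection as censoring assumes that patients who stop have the same later risk as those who continue. Treating it as a competing event leaves the estimate dependent on stopping.
2. As a supplement, exposure-adjusted incidence: patients with a first event divided by patient-months from first dose to the first event or 30 days after the last dose, with the arm difference and a confidence interval. Note that it assumes a roughly constant hazard.

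State that between-arm differences in crude incidence are to be read alongside these tables. AE onset dates (Section 14.5) and dosing records (Section 10.4) are already collected, so the cost is SAP wording and a few more tables. Trial conduct does not change.
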